14.5. Primary Analysis

Primary efficacy analysis:

Binocular, high luminance, high contrast logMAR visual acuity will be analyzed using a linear mixed model. The model will include the experimental design factors: distance (distance/intermediate/near) and time point (2 week or 4 week) as fixed effects; and site and subject nested in site as random effects. Other baseline characteristics known to be important such as age, gender, subject group (myope/hyperope), and/or ADD power will be included as fixed covariates when appropriate. The covariance between residual errors from the same subject at the same time point across distances will be selected based on the finite-sample corrected Akaike's Information Criterion.⁶ Covariance structures considered will include: Homogenous Compound Symmetry (CS), Heterogeneous Compound Symmetry (CSH), and Unstructured covariance structure (UN). The structure that returns the lowest Akaike Information Criteria Corrected (AICC) will be selected as the structure that best fit the data. Heterogeneous models across study populations and/or distance will be considered using a log-likelihood ratio test.

Comparisons will be carried out using 95% confidence intervals (CIs) constructed of Least-square means (LSM) from the linear mixed models. Statistical superiority will be concluded if the upper limit of the confidence intervals of the Test lens is below +0.10 logMAR for distance, and below +0.17 logMAR for intermediate and near.

CLUE Vision

Overall quality of vision scores will be analyzed using a linear mixed model adjusting for baseline values as fixed covariates. The model will include the experimental design factors: time point (2 week or 4 week) as the fixed effect; and site and subject nested in site as random effects. Other baseline characteristics known to be important such as age, gender, subject group (myope/hyperope), and/or ADD power will be included as fixed covariates when appropriate. The covariance between residual errors from the same subject across lens wearing periods/time point will be selected based on the finite-sample corrected Akaike's Information Criterion.⁶ Covariance structures considered may include: Homogenous compound symmetry (CS) and Unstructured covariance structure (UN). The structure that returns the lowest Akaike Information Criteria Corrected (AICC) will be selected as the structure that best fit the data.

Primary Hypothesis:

Comparisons will be carried out using 95% confidence intervals constructed of least-square means (LSM) from the linear mixed models of CLUE vision scores at the end of first wearing cycle (2 week). Statistically superiority will be concluded if the lower limit of the confidence intervals of the test lens are greater than 32 points.

Secondary Hypothesis:

Comparisons between the wearing cycles (2 week vs 4 week) will be carried out using 95% confidence intervals constructed of least-square means (LSM) differences (4 week – 2 week) from the linear mixed model. The superiority will be established if the lower confidence limit is above 0.

In all models, the Kenward and Roger method⁷ will be used for the calculation of the denominator of degrees of freedom.

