14.2. Sample Size Justification

A total of 80 subjects (48 myopes and 32 hyperopes) are targeted to complete the study.

Using the POWER procedure in SAS 9.4, below is the summary of sample size required based on the different assumptions of the true LogMAR visual acuity and CLUE scores. The sample size was calculated for the non-inferiority tests (using 0.05 as the margin) with at least 90% of statistical power and 2-sided type I error of 0.05. Assuming the true LogMAR visual acuity is between 0.00 to 0.05 (distance) or 0.08 to 0.12 (near), and true CLUE vision score is between 38 to 42 points.

- Binocular LogMAR visual acuity (distance)

True Value	Estimated Standard Deviation	# of subjects needed	Actual Power
0.00	0.12	18	0.915
0.02	0.12	26	0.904
0.05	0.12	63	0.902

- Binocular LogMAR visual acuity (intermediate and near)

True Value	Estimated Standard Deviation	# of subjects needed	Actual Power
0.08	0.12	21	0.905
0.10	0.12	33	0.901
0.12	0.12	63	0.902

- CLUE vision score

True Value	Estimated Standard Deviation	# of subjects needed	Actual Power
38	17	87	0.902
40	17	50	0.903
42	17	33	0.906

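### The 90% power in Section 14.2 is that of one-sample t-tests, not of the planned random-site model: CLUE 38 misses it in any case, and three other rows may if sites are few

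*Combined protocol and SAP*

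**What the plan says.** **Sizing (Section 14.2).** The calculation was done "Using the POWER procedure in SAS 9.4", "with at least 90% of statistical power and 2-sided type I error of 0.05". Its inputs are a true value, an SD and a number of subjects. It makes no allowance for site, clustering or degrees of freedom. For the patient-reported endpoint it assumes the "true CLUE vision score is between 38 to 42 points". The target is 80 completers, yet the CLUE 38 row of the same table asks for 87.

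**Analysis (Section 14.5).** The acuity and CLUE models both include "site and subject nested in site as random effects". In every model the Kenward-Roger method "will be used for the calculation of the denominator of degrees of freedom". Each primary decision compares one limit of a 95% confidence interval for a single-arm mean with a fixed threshold: +0.10 logMAR for distance, +0.17 for intermediate and near, and 32 CLUE points at the end of the first wearing cycle.

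**Gating (Section 2.3).** The secondary hypothesis is tested only if all four primary hypotheses succeed.

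**Number of sites.** It is not given. The synopsis says the site list is kept in the Trial Master File. More than one site is implied by the random site term and by the contrast-sensitivity test being confined to Site 1036.

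**The concern.** In a randomised comparison, site variance largely cancels from the treatment difference. Here there is no second arm, so it enters the standard error of the mean in full. A second effect does not need real site differences. Whenever the estimated site variance is positive, the Kenward-Roger degrees of freedom for the mean drop towards the number of sites minus one, and with few sites the interval widens sharply. Section 14.2 allows for neither.

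At stake is whether the power figures that justify 80 subjects describe the analysis that will be run. One missed primary hypothesis also blocks the secondary, and no joint power is given.

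**Working it through.** **1. Reproducing the table.** Inputs from Section 14.2: SD 0.12 logMAR or 17 CLUE points, two-sided 5%. Thresholds from Section 14.5: 0.10, 0.17 and 32. With δ = |threshold − true value|, power is that of a two-sided one-sample t-test: noncentral t, n − 1 df, noncentrality λ = √n × δ/SD.

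| Row | δ | n in plan | Power in plan | Recomputed at that n | t-test at N=80 |
|---|---|---|---|---|---|
| Distance 0.00 | 0.10 | 18 | 0.915 | 0.915 | >0.99 |
| Distance 0.02 | 0.08 | 26 | 0.904 | 0.904 | >0.99 |
| Distance 0.05 | 0.05 | 63 | 0.902 | 0.902 | 0.957 |
| Int./near 0.08 | 0.09 | 21 | 0.905 | 0.905 | >0.99 |
| Int./near 0.10 | 0.07 | 33 | 0.901 | 0.901 | >0.99 |
| Int./near 0.12 | 0.05 | 63 | 0.902 | 0.902 | 0.957 |
| CLUE 38 | 6 | 87 | 0.902 | 0.902 | **0.877** |
| CLUE 40 | 8 | 50 | 0.903 | 0.903 | 0.986 |
| CLUE 42 | 10 | 33 | 0.906 | 0.906 | >0.99 |

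For CLUE 38 at N=80, λ = √80 × 6/17 = 3.16, giving 0.877. All nine rows match, so the sizing is a plain t-test on independent subjects. (Section 2.3 prints +0.01 for distance. The table fits only +0.10. That is a separate inconsistency.)

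**2. Adding the site term, one value per subject.** Assume k equal sites. Then Var(mean) = σ²_site/k + σ²_within/N. If the between-site mean square exceeds the within-site one, SE = √(MS_site/N) with k − 1 df. Otherwise the site component drops out and df = N − 1. The critical value with 4 sites is 3.18 (3 df), against 1.99 with 79 df. With no true site variance, the estimate is still positive in about 37% of trials (3 sites) to 45% (10 sites).

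Simulated power, N=80, true site variance zero:

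| Sites | Distance 0.05, int./near 0.12 | CLUE 38 | CLUE 40 |
|---|---|---|---|
| No site term | 0.957 | 0.877 | 0.986 |
| 3 | 0.63 | 0.56 | 0.68 |
| 4 | 0.73 | 0.62 | 0.81 |
| 5 | 0.80 | 0.68 | 0.88 |
| 6 | 0.85 | 0.72 | 0.92 |
| 8 | 0.89 | 0.77 | 0.95 |
| 10 | 0.91 | 0.79 | 0.96 |

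The other five rows stay at or above 0.92 with 4 or more sites. True site variance makes the loss larger: at an assumed ICC of 0.02 with 5 sites, the 0.05-logMAR rows fall to 0.70 and CLUE 38 to 0.57.

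**3. Closer to the planned model: two visits per subject.** Further assumptions: within-subject correlation 0.3–0.7; CLUE taken at week 2; the acuity mean averaged over both visits, since Section 14.5 names no visit for it; Satterthwaite-type df, taken as equal to Kenward-Roger in balanced data; site variance zero. The acuity ranges also cover different assumptions about how the remaining variance is split.

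| Sites | Distance 0.05, int./near 0.12 | CLUE 40 |
|---|---|---|
| 3 | at most 0.86 | 0.76–0.86 |
| 4 | 0.78–0.94 | 0.87–0.93 |
| 6 | 0.88–0.98 | 0.94–0.96 |
| 8 or more | at least 0.91 | at least 0.96 |

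CLUE 38 is 0.60–0.84 over 3–10 sites.

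**4. Baseline adjustment of CLUE.** If baseline and follow-up correlate at 0.5 (assumed), the SD becomes 17 × √(1 − 0.25) = 14.7. CLUE 38 then has power 0.78–0.85 with 4 sites and 0.90–0.92 with 8.

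**The case against.** A reader might infer that the planned analysis fails to deliver 90% for several tabled rows as a matter of fact, or that the trial as a whole is underpowered. The documents do not support either reading. The number of sites is unknown, and with 8 or more sites and repeated visits modelled only CLUE 38 falls short. That row's failure is already visible as 87 against 80; the site term deepens it but does not cause it. Most rows need 18 to 63 subjects, so 80 leaves reserve. Two model features left out of the sizing help power: averaging acuity over visits and adjusting CLUE for baseline. These points stand and limit the claim. The gain from adjustment is uncertain, because the plan does not say whether the SD of 17 is already adjusted.

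It can also be said that the 90% describes how each row's n was found and makes no promise about the mixed model at N=80, and that sizing by t-test is a common simplification. That is a fair reading of the sentence. But the table is the only justification given for 80 subjects, and the simplification is less harmless in a single-arm trial, where nothing cancels the site component.

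No bias or type I error inflation follows from any of this. The random site term itself is not at fault.

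**Conclusion.** The point holds in a limited form. The mismatch between sizing and analysis is certain from the documents. So is the CLUE 38 shortfall, which exists before any site term is added.

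For distance 0.05, intermediate/near 0.12 and CLUE 40, the shortfall is conditional on few sites: about 3–6 for acuity and 3–4 for CLUE 40, with no true site variance and repeated visits modelled. It reaches further with one value per subject or with real site differences. The other five rows are safe at N=80 given 4 or more sites and no true site variance.

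These figures assume equal-sized sites, the within-subject correlations shown, and that a zero site-variance estimate simply drops that component. Neither the site count nor any ICC comes from the documents.

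**What to change.** In Section 14.2:

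- State the number of sites.
- Restate power at N=80 from a simulation of the planned mixed model: repeated visits, CLUE baseline adjustment, random site and Kenward-Roger df. Use a stated ICC range, for example 0 to 0.05, and say whether the SD of 17 is before or after baseline adjustment.
- Report power for each endpoint and jointly for the four primary hypotheses.
- Drop the claim of at least 90% for any row that does not reach it. CLUE 38 is about 88% at N=80 even under the t-test.

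The cost is a short simulation and a less favourable stated power. No extra subjects or procedures are needed, and the analysis model need not change. If the site count is large enough, the simulation will support most of the table.

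### The acuity model's single subject intercept only partly captures re-measurement of the same distance at Visits 2 and 4, so the standard errors that decide hypotheses 1–3 may be wrong

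*Combined protocol and SAP*

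**What the plan says.** Section 14.5 (Primary Analysis, acuity) fits a linear mixed model with "distance (distance/intermediate/near) and time point (2 week or 4 week) as fixed effects; and site and subject nested in site as random effects". No distance-by-time interaction is listed. On top of the random effects, "The covariance between residual errors from the same subject at the same time point across distances will be selected" by AICC from CS, CSH and UN. The section adds that models heterogeneous across populations and/or distance will be examined by likelihood ratio test, and applies Kenward–Roger degrees of freedom in every model.

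The decision rule rests on the LSM interval alone: "Comparisons will be carried out using 95% confidence intervals (CIs) constructed of Least-square means (LSM) from the linear mixed models". Superiority requires the upper limit to fall "below +0.10 logMAR for distance, and below +0.17 logMAR for intermediate and near".

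For CLUE, the same section again uses random site and subject effects and states: "The covariance between residual errors from the same subject across lens wearing periods/time point will be selected", with CS or UN over the two time points.

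Three other sections matter here. Section 2.3 words acuity hypotheses 1–3 as after 10 to 14 days of wear without naming a visit, whereas the CLUE hypothesis names Visit 2. Section 4.1 says the second cycle uses new lenses of the same power, without optimisation. Step 1.21 of Section 7.2 gives the distance correction to the dominant eye and the near correction to the other.

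**The concern.** Each subject contributes six binocular acuities: three distances at two visits. Under the written model, residuals from different visits are independent given the subject intercept. Every cross-visit pair therefore gets the same covariance, the subject variance. Distance at Visit 2 is tied to distance at Visit 4 no more closely than it is to near at Visit 4.

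Some subjects may see consistently well at far and less well at near, or the reverse. That pattern should persist when the same powers are re-dispensed, and same-distance pairs will then correlate more strongly than different-distance pairs. The three residual structures shape only the 3×3 block within a visit, so AICC cannot select a structure that separates the two kinds of pair.

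Distance and time point are additive, so each distance LSM draws on both visits and its standard error uses this cross-visit covariance. At stake is the 2.5% one-sided error of the limits that decide hypotheses 1–3, and so the 5% overall rate in Section 14.4.

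**Working it through.** **Inputs from the documents.** n = 80 and SD 0.12 (Section 14.2); limits +0.10 and +0.17 (Section 14.5); per-protocol analysis requiring all visits (Sections 14.1 and 14.3), so the data are essentially balanced.

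**Assumed inputs.** The documents give no retest or cross-distance correlation, so ranges are used. Site variance is set to zero and results are large-sample.

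**The plan's own figure first.** A one-sample t-test with two-sided alpha 0.05, SD 0.12, true value 0.05 and limit +0.10 gives n = 63 with power 0.902, as in Section 14.2. The other rows also reproduce. This calculation uses one value per subject and says nothing about cross-visit covariance. It needs +0.10 for distance; the +0.01 in Section 2.3 is a separate inconsistency to reconcile.

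**Equal components at the three distances.** Let c be the same-distance retest correlation and b the cross-visit correlation between different distances. With balanced data the distance LSM is the two-visit mean.

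- True variance: s²(1 + c)/(2n).
- The fitted model has one cross-visit value v. Of the nine cross-visit pairs, three have c and six have b, so v = (3c + 6b)/9 = (2b + c)/3.
- Model variance: s²(1 + v)/(2n).
- SE ratio (model/true): √[(1 + v)/(1 + c)].
- One-sided error: Φ(−1.96 × ratio).

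The first number in each set is the same-visit cross-distance correlation, which cancels from the ratio.

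| Set (same-visit / b / c) | v | SE ratio | One-sided error |
|---|---|---|---|
| 0.6 / 0.5 / 0.8 | 0.600 | √(1.600/1.800) = 0.943 | Φ(−1.848) = 3.2% |
| 0.3 / 0.2 / 0.7 | 0.367 | √(1.367/1.700) = 0.897 | Φ(−1.758) = 3.9% |
| 0.2 / 0.1 / 0.8 | 0.333 | √(1.333/1.800) = 0.861 | Φ(−1.688) = 4.6% |
| b = c | c | 1.000 | 2.5% |

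Minimising the expected Gaussian likelihood of the written model with a UN block gives the same ratios. A Visit 2 LSM from the additive model gives 0.947, 0.906 and 0.871 for the first three sets.

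**On the logMAR scale.** With c = 0.8 the true half-width is 1.96 × 0.12 × √(1.8/160) = 0.0249. The model would report 0.0249 × 0.943 = 0.0235, or 0.0249 × 0.861 = 0.0214.

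**Unequal components.** Total variance is 1 at each distance. It is split into a subject share, a stable subject-by-distance share, and visit-level error for the remainder. The same likelihood fit with a UN block gives:

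| Subject share | Subject-by-distance shares | SE ratios | One-sided errors |
|---|---|---|---|
| 0.4 | 0.05 / 0.20 / 0.35 | 1.055 / 0.978 / 0.891 | 1.9% / 2.8% / 4.0% |
| 0.3 | 0.40 / 0.05 / 0.40 | 0.898 / 1.086 / 0.898 | 3.9% / 1.7% / 3.9% |
| 0.3 | 0 / 0.10 / 0.40 | 1.078 / 1.024 / 0.861 | 1.7% / 2.2% / 4.6% |
| 0.4 | 0.10 / 0.30 / 0.10 | 1.010 / 0.902 / 1.010 | 2.4% / 3.9% / 2.4% |

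Adding a subject-by-distance effect with a separate variance for each distance returns every ratio in both tables to 1.000.

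**CLUE.** Two visits identify one variance and one covariance under CS (2 moments), or two variances and one covariance under UN (3). A random subject effect plus residual CS or UN has 3 or 4 parameters, one too many. The marginal covariance is still an ordinary CS or UN matrix, so the LSM standard errors do not depend on how it is split.

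**The case against.** **The repeat visits are already modelled.** A reader of the residual-covariance sentence alone might infer that the plan ignores re-measurement. It does not: the plan includes "and site and subject nested in site as random effects", and the subject effect is shared by all six records. If the between-visit correlation is purely at subject level, the standard errors are correct. What remains is the narrower restriction, that same-distance and different-distance pairs share one value.

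**The direction is not fixed.** A reader might also infer that all three intervals are too narrow and that the error always favours success. That holds only if the distance-specific component is similar at each distance. With unequal components at least one interval is too wide in every case computed, including the pattern monovision might suggest, with far and near each dominated by one eye and intermediate not.

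**Practical effect is small near the planning values.** At the least favourable planned values (0.05 against 0.10; 0.12 against 0.17), power moves from roughly 97.5–98% to 98–99%. This stands. The issue bears on error control close to the limits, and the trial is unlikely to fail because of it.

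**The plan may already allow a remedy.** The likelihood-ratio sentence on heterogeneity could be stretched to cover a subject variance that differs by distance. It does not say so, and heterogeneous residual variances alone add no same-distance cross-visit term.

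**Week 2 may be intended.** With a distance-by-time interaction, a week-2 LSM has ratio 1.000 in the equal-component scenarios. Section 14.5 lists no interaction, and the first unequal case still gives 1.060 / 1.021 / 0.948 under UN.

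**Conclusion.** The point holds as a conditional misspecification. The written model cannot represent a stable distance-specific component, and neither AICC over the listed structures nor Kenward–Roger repairs that. Such a component is plausible from the design, but the documents neither show nor quantify it.

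Under equal components and the assumed correlations, standard errors are 6–14% too small, with one-sided error 3.2–4.6%. Under unequal components the ratios run from about 0.86 to 1.09, in both directions. With equal cross-visit correlations nothing is lost. The error rate of hypotheses 1–3 therefore depends on an untested restriction that is cheap to remove.

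The CLUE redundancy is a tidy-up only. A reader might take it to invalidate the CLUE intervals, but their standard errors are unaffected.

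**What to change.** **Acuity, Section 14.5.** Use one of the following, and let AICC choose only among structures that contain the same-distance cross-visit term:

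- Add a random subject-by-distance effect whose variance may differ by distance, keeping the subject intercept and the within-visit residual block. With a UN block this is 1 + 3 + 6 = 10 subject-level covariance parameters, against 1 + 6 = 7 now. It reduces to the current model if the extra variances are zero.
- Replace the subject intercept and the residual block with an unstructured 6×6 covariance over the six distance-by-visit measurements (6 × 7/2 = 21 parameters).

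A direct-product structure such as UN@UN is a more economical candidate, but it should not be the only one. It sets the cross-visit covariance of two distances to one factor times their same-visit covariance. If every correlation is 0.6, a factor of 0.6 implies 0.6 × 0.6 = 0.36 across visits for different distances, so it does not even contain the current model.

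The section should also name the visit at which the acuity LSMs are tested and say whether a distance-by-time interaction is included.

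**CLUE (minor).** Keep either the random subject effect or the residual CS/UN over the two visits.

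**Cost.** A few sentences in Section 14.5 and a few lines of SAS. There are more covariance parameters to estimate from 80 subjects, so a fallback for non-convergence should be stated. Intervals may widen or narrow to their correct width.

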2.3. Hypotheses

The following primary hypotheses will be tested throughout this investigation.

Primary Hypotheses:

1. After 10 to 14 days of wear, the distance, binocular, high luminance, high contrast visual acuity score for the Test lens will be statistically better than +0.01 logMAR.
2. After 10 to 14 days of wear, the intermediate, binocular, high luminance, high contrast visual acuity score for the Test lens will be statistically better than +0.17 logMAR.
3. After 10 to 14 days of wear, the near, binocular, high luminance, high contrast visual acuity score for the Test lens will be statistically better than +0.17 logMAR.
4. After the first 10 to 14 days of wear, the PRO CLUE vision scores for the Test lens will be statistically better than 32 CLUE points. This will be recorded by the subject using the CLUE Follow-up Questionnaire from Visit 2.

If all the primary hypotheses are met, the following secondary hypotheses will be tested.

Secondary Hypotheses:

The PRO CLUE vision scores after the second 10 to 14 days wear cycle (Visit 4) will be statistically better than the score after the first 10 to 14 days wear cycle (Visit 2). This will be recorded using the CLUE Follow-up Questionnaire.

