4.2. Study Design Rationale

The study is intended to evaluate the initial performance, of a photochromic lens fit as monovision, in terms of the subjective response and visual acuity, after a period of lens dispensing. The single-ARM study is used as the performance will be measured against historical performance measures used in previous multifocal contact lens studies. A washout period and lens re-dispensing was used to evaluate the reproducibility and repeatability of the subjective vision response.

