7.2. Detailed Study Procedures

VISIT 1

Subjects must report to the visit wearing their habitual contact lenses to accurately assess baseline PRO (CLUE) performance. If the subject is not wearing their lenses they must be rescheduled.

Visit 1: Screening			
Step	Procedure	Details	
1.1	Statement of Informed Consent	Each subject must read, understand, and sign the Statement of Informed Consent before being enrolled into the study. The Principal Investigator or his/her designee conducting the informed consent discussion must also sign the	

		consent form. Note: The subject must be provided a signed copy of this document.	
1.2	Demographics	Record the subject's age, gender, race and ethnicity.	
1.3	Medical History and Concomitant Medications	Questions regarding the subjects' medical history and concomitant medications.	
1.4	Habitual Lenses	Questions regarding the subject's habitual lens type and parameters.	
1.5	Contact Lens History	Record the subject's correction type (i.e. monovision, multifocal, sphere with readers, etc.).	
1.6	Wear time and Comfortable Wear time with Habitual lenses	Record the subjects wear time and comfortable wear time with their habitual contact lenses.	
1.7	Eligibility after Screening	All responses to Screening Inclusion Criteria questions must be answered "yes" and all responses to Exclusion Criteria must be answered "no" for the subject to be considered eligible.	

Visit 1: Baseline			
Step	Procedure	Details	
1.8	Baseline PRO (CLUE and MRD) and CLDEQ-8 Questionnaires	The subject will evaluate the vision characteristics, comfort characteristics, handling characteristics, and visual symptoms of their habitual lenses using the PRO (CLUE and MRD) questions.	
1.9	Ocular Symptoms	Subjects will respond to a verbal open-ended symptoms questionnaire.	
1.10	Entrance Visual Acuity	Distance and near Snellen visual acuity will be measured for each eye with the subject's habitual contact lenses in place. For near measures use the ETDRS 2000 Series Chart 1 or 2. The acuity will be recorded to the nearest letter OD, OS and OU.	
1.11	Binocular Contrast Sensitivity (CS) Measurement (Site 1036 only)	Measure the subject's Binocular CS at 4M, distance. The measurement is made using the attached work aid. See section 4 to set the trial number (set to 25) and section 5 to execute the test.	Appendix G
1.12	Lens Removal	Have the subject remove their habitual lenses and store in an approved storage solution.	

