		
lenses if any of the following is observed:
 
 presence of limbal exposure (appearance of clear cornea) in any gaze presence of edge lift presence of unacceptable movement (excessive or insufficient) in all three movement categories (primary gaze, upgaze, and push-up). 
If either lens is deemed unacceptable, the subject will be discontinued from the study. Remove the lenses, perform a slit-lamp evaluation, and complete the Final Evaluation form.
	
2.12	Lens Removal	
Have the subject remove the study lenses and store in saline in a labeled glass vial.
 
Note: Lenses do not need to be stored in a refrigerator.
	
2.13	Biomicroscopy	
Perform biomicroscopy OD and OS. Slit Lamp Classification Scales will be used to grade the findings.
 
For the conjunctival redness [REDACTED] 0.5 unit increments will be used in the grading.
 
Corneal Staining Assessment [REDACTED] will be graded in 1.0 increments.
 
If the clearance of the fluorescein needs to be expedited, preservative-free rewetting drops or saline may be instilled.
	[REDACTED] [REDACTED] [REDACTED]
2.14	Exit Visual Acuity	
Distance and near Snellen visual acuity will be measured for each eye with the subject's habitual correction lenses in place.
 
For near measures use the ETDRS 2000 Series Chart 1 or 2. The acuity will be recorded to the nearest letter OD, OS and OU.
	[REDACTED]
2.15	Subject Instructions	
Subjects will complete a wash out period of 7 ± 3 days.
 
Instruct the subjects they can wear their habitual contacts or glasses during the washout period.
	
2.16	Schedule Next Visit	The subject will be scheduled to return for their next visit in 4-10 days.	

VISIT 3

Subjects must report to the visit wearing their habitual contact lenses to accurately assess baseline PRO (CLUE) performance. If the subject is not wearing their lenses they must be rescheduled.

Visit 3: Baseline			
Step	Procedure	Details	
3.1	Adverse Events and Concomitant Medications Review	
Review the subject's concomitant medications and record any changes from the previous study visit.
 
Record any adverse events or medical history changes from the previous study visit.
	
3.2	Baseline PRO (CLUE Questionnaire)	The subject will evaluate the vision characteristics, comfort characteristics, handling characteristics, and visual symptoms of their habitual lenses using the PRO (CLUE) questions.	

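### Is the baseline-adjusted CLUE interval too narrow to be tested against a fixed 32 in a single-arm trial?

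*Combined protocol and SAP*

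**What the plan says.** The CLUE part of Section 14.5 (Primary Analysis) reads "Overall quality of vision scores will be analyzed using a linear mixed model adjusting for baseline values as fixed covariates". The remaining model terms are "time point (2 week or 4 week) as the fixed effect; and site and subject nested in site as random effects", with age, gender, subject group and ADD power added where appropriate, and Kenward-Roger degrees of freedom. The decision rule uses the 2-week least-squares mean: "Statistically superiority will be concluded if the lower limit of the confidence intervals of the test lens are greater than 32 points".

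Three other places bear on what that mean is meant to represent:

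- Section 2.3, hypothesis 4: "the PRO CLUE vision scores for the Test lens will be statistically better than 32 CLUE points".
- Section 4.2: "The single-ARM study is used as the performance will be measured against historical performance measures used in previous multifocal contact lens studies".
- Section 14.2 assumes that the "true CLUE vision score is between 38 to 42 points", with SD 17.

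Section 7.2 collects habitual-lens CLUE twice before a fitting. At Visit 1 (step 1.8) the subject rates "visual symptoms of their habitual lenses using the PRO (CLUE and MRD) questions", and at Visit 3 (step 3.2) "visual symptoms of their habitual lenses using the PRO (CLUE) questions". Section 14.5 does not say which of the two is the baseline covariate.

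**The concern.** In a two-arm trial, adjusting for baseline sharpens the difference between arms, and sampling variation in the mean baseline largely drops out of that difference. Here there is one arm and the comparator is a constant, so it does not drop out. A least-squares mean evaluated at the sample mean baseline has a model standard error that conditions on that mean. Kenward-Roger does not add the missing component, because it deals with estimated variance components and degrees of freedom.

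If the intended quantity is the mean score in a wider population of monovision wearers, the interval is too short. The interval limit is the whole CLUE decision rule, so the error of this test in the success direction could exceed 2.5%. The benchmark from other studies, a hypothesis that does not mention baseline, and a sample size that behaves like a plain one-sample test all suggest a population mean. The plan states neither the target nor which baseline enters the model.

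**Working it through.** **Inputs from the documents.** Reference 32 (Sections 2.3 and 14.5); SD 17, assumed true means 38, 40 and 42, two-sided 0.05, at least 90% power, 80 completers (Section 14.2). **Assumed, because the documents give none:** the baseline to follow-up correlation rho (0.3, 0.5, 0.7), the number of sites (4 to 10) and the site intraclass correlation (ICC, 0 to 0.05).

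**1. The plan's own figures.** A one-sample t test against 32 has noncentrality (true mean - 32)/17 x sqrt(n).

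| True mean | n | Noncentrality | Power | Printed |
|---|---|---|---|---|
| 38 | 87 | 6/17 x sqrt(87) = 3.29 | 0.902 | 0.902 |
| 40 | 50 | 8/17 x sqrt(50) = 3.33 | 0.903 | 0.903 |
| 42 | 33 | 10/17 x sqrt(33) = 3.38 | 0.906 | 0.906 |

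The table reproduces. It does not settle the target, because Section 14.2 does not say whether 17 is a raw or a residual SD.

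**2. Size without any site effect (upper bound).** For a population mean the standard error at n = 80 is 17/sqrt(80) = 1.90, and the half-width is 1.99 x 1.90 = 3.78. The adjusted standard error is 1.90 x sqrt(1 - rho^2). One-sided error for a population mean is 1 - Phi(1.96 x sqrt(1 - rho^2)).

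| rho | sqrt(1 - rho^2) | Adjusted half-width | One-sided error, formula | Simulated (100,000 runs) |
|---|---|---|---|---|
| 0.3 | 0.954 | 3.61 | 3.1% | 3.1% |
| 0.5 | 0.866 | 3.28 | 4.5% | 4.4% |
| 0.7 | 0.714 | 2.70 | 8.1% | 8.0% |

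In the same simulations, measured against the mean at the observed baselines, the error was 2.5% at every rho. The interval is valid for that target.

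**3. Size under the planned model.** Section 14.5 includes random site. Estimating a site variance from few sites widens the interval and offsets part of the shortfall. In simulation (both time points, random site and subject, correlation between visits 0.7), one-sided error for a population mean was:

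- rho 0.3: 1.8-3.1%
- rho 0.5: 2.7-4.2%
- rho 0.7: 4.1-7.3%

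A simpler Visit-2-only version with 4 or 8 sites and ICC 0 or 0.02 gave 2.0-2.4%, 2.7-3.6% and 4.8-6.0%.

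**4. What the alternative costs.** Dropping baseline and keeping only design terms gave errors of 1.4-2.9% in the full model and 1.4-2.2% in the simpler one, so it tends to be conservative. With no site term or site variance, power at a true mean of 38 and n = 80 is about 88% unadjusted against 92% adjusted at rho 0.5. With random site and ICC 0.02, the simpler version gives 70% against 79% (8 sites) and 49% against 58% (4 sites), a loss of about 9 points. If a population mean is meant, some of the adjusted test's advantage comes from its larger error, so these are not powers at equal error.

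**5. Which baseline.** At rho 0.5 the error was 2.8-4.2% with the Visit 1 score and 2.7-4.1% with each cycle's own baseline. The choice hardly matters, and only the Visit 1 score precedes the Visit 2 outcome.

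**The case for a change.** The strongest case for a change is that a population mean is the more natural reading of Sections 2.3, 4.2 and 14.2, that Section 14.4 claims an overall 5% error rate, and that one sentence would settle the matter before database lock. The variance argument is correct for that reading, and at rho 0.7 the inflation is clear. That much stands.

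It does not show an error in the plan. None of the three places is conclusive. The documents do not say whether the historical 32 came from raw means or from baseline-adjusted ones; if adjusted, the planned analysis compares like with like. Conditioning on observed covariates is the usual convention for least-squares means. Clear inflation needs a strong correlation between ratings of the habitual lenses and ratings of a different study lens, and nothing in the documents supports a particular value.

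The remedy is not free either, as step 4 shows. Section 2.3 also lists four primary hypotheses, and all must be met before the secondary is tested, so the chance of wrongly passing all four is no larger than that for CLUE alone. Finally, Section 14.1 promises n, mean and SD for the efficacy variables. If these are tabulated by visit, a reader who wants the simple unadjusted interval, without site variance, can compute it as mean ± t x SD/sqrt(n).

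**Conclusion.** The concern does not call for a change. The planned interval is valid for the mean at the observed baselines. For a population mean it runs from about nominal at rho 0.3 to roughly 3-4% at 0.5 and 4-7% at 0.7 under the planned random-site model. All of these rest on assumed correlations, site numbers and site variance. Replacing a conventional baseline-adjusted mean with an unadjusted one would trade that possible excess for a test that is often conservative and, with modest site variance at rho 0.5, has about 9 points less power at a true mean of 38. That is a fair trade-off on which competent statisticians differ. The unstated target and the unnamed baseline visit are missing detail: an analyst would take Visit 1 as the baseline for the Visit 2 test, and the choice has almost no effect on it.
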